8.2 Assessment of Adverse Events

The occurrence of AE/SAE (drug- or procedure or study-related) will be assessed by non-directive questioning of the patient since the beginning of the study at the screening Period, and

PREOB-ON3 - Clinical Study Protocol

PREOB-ON3-CSP	V 6.1	Author: [name]	May 15, 2017	Pg. 71/72
---------------	-------	----------------	--------------	-----------

each follow-up visit searching for any changes in health status (e.g., "Have any Adverse events or Serious adverse events occurred since the last visit?"). Furthermore, AE/SAE spontaneously reported by the patient during or between the follow-up visits, or detected through observation, physical examination (including body mass index and vital signs), laboratory testing, or other clinical procedures during the observation period will be documented. Patients will be instructed that they must immediately report any adverse events, subjective complaints, or objective changes in their wellbeing to the investigator or the Investigating Site's personnel, regardless of the perceived relationship between the event and the test product.

If it is determined that an AE/SAE has occurred, the Investigator should obtain all the information required to complete the corresponding AE or SAE Form of the eCRF, and establish potential causality relationship with the product or study procedures, including the bone marrow harvesting, the blood sampling and the product implantation (core decompression, implantation surgery, and general anaesthesia).

8.2.1 Observation period for the occurrence of AEs and SAEs

Table 11 below defines the observation period for the occurrence of AE and SAE during both the follow-up period (up to 24 months) and the long term follow-up (at 36 and 48 months). These safety observation periods must be respected for all treated patients (*i.e.*, regardless of the patient's outcome in the study, whether the patient has been withdrawn/discontinued early or not).

Table 11: Observation period for the occurrence of AEs and SAEs

Follow-up: AE/SAE Observation Period	From Screening Period up to 24 months after implantation (Visit 3)
Long term follow-up: AE/ SAE Observation Period	At 36 and 48 months after implantation (Visit 3)

If the investigator learns of any SAE, including a death, any time after the two defined observation period for the occurrence of AEs and SAEs (Table 11), and considers the event reasonably related to the Investigational Medicinal Product, the investigator will promptly notify the Study contact for reporting SAEs.

PREOB-ON3 - Clinical Study Protocol

PREOB-ON3-CSP

V 6.1

Author: [name]

May 15, 2017

Pg. 72/73

8.2.2 *Summary of Possible Risks related to the Procedures*
Table 12: Summary of Possible Risks related to the Procedures

	AE	SAE (Fatal and Non-Fatal)
Bone Marrow Harvest	Pain at the aspiration site Local haematoma	-
Bone Marrow Concentrate/Mesenchymal Stromal Cells Implantation	Fever	-
Core Decompression and Implantation Procedure	Surgery Pain at the implantation site Local haematoma Infectious complications General anaesthesia Transient hypotension Nausea and vomiting	Surgery Femoral neck fracture Femoral head blow-up Haemorrhage Sepsis Shock General anaesthesia Cardiac complications 
 • Myocardial infarction • Cardiopulmonary arrest • Ventricular tachycardia Neurological complications 
 • Stroke Pulmonary complications 
 • Inhalation pneumonia • Pulmonary embolism Anaphylactic shock
Blood Sampling	Pain at the sampling site Local haematoma Superficial vein thrombosis Transient hypotension/lypothermia	Syncope

PREOB-ON3 - Clinical Study Protocol

PREOB-ON3-CSP | V 6.1 | Author: [name] | May 15, 2017 | Pg. 73/74

8.2.3 Summary of Observed Adverse Events (AE) and Serious Adverse Events (SAE) possibly related to Study Treatment in Osteonecrosis

Table 13: Summary of Observed Adverse Events (AE) and Serious Adverse Events (SAE) possibly related to Study Treatment (i.e., PREOB® and/or to the Implantation Procedure) (33 subjects (hips)*)

Non-Serious AE	SAE (Non-Fatal)
Total	9.1%
Fever	9.1%
	Total
	6.1%
	Systemic inflammatory response syndrome
	3.0%
	Pancytopenia**
	3.0%
	Pyrexia**
	3.0%
	Altered status of consciousness**
	3.0%
	Hypotension**

* Based on the Phase IIb study with the product under investigation in osteonecrosis. For more detailed information, see the Investigator's Brochure. AEs and SAEs were limited to treatment emergent adverse events (TEAEs) and serious treatment emergent adverse events (STEAEs) and reported per Preferred Term (PT) (MedDRA coding), along with their frequency of occurrence in subjects. Subjects were counted once for each PT. An AE/SAE was considered as treatment-emergent if it occurred on or after the date of the IMP implantation. In case of missing start date, the AE was considered as treatment-emergent

** 4 SAEs were reported in the same patient.

8.3 Management of Safety Issues

- In the event of an AE/SAE, the Investigator will immediately initiate appropriate therapy and management according to his/her medical judgment and will decide whether to withdraw the patient from the study.
- The patient must be followed-up by additional examinations according to the medical judgment of the Investigator, until the AE/SAE and/or abnormal condition is resolved or the Investigator deems further observations or examinations are no longer medically indicated.

8.3.1 Safety Data Notification Reporting, and Monitoring

8.3.1.1 Reporting of Adverse Events (AEs)

All AEs will be recorded on the appropriate and corresponding AE Form of the eCRF by the Investigator. All AEs must be reported whether or not considered causally related to the IMP or any related study procedures. For every AE, the Investigator will provide an assessment of

PREOB-ON3 - Clinical Study Protocol

PREOB-ON3-CSP	V 6.1	Author: [name]	May 15, 2017	Pg. 74/75
---------------	-------	----------------	--------------	-----------

the severity and causal relationship to the IMP or any related study procedures and document all actions taken with regard to the IMP, and any other treatment modalities for the AE. Treatment of any AE is at the sole discretion of the investigator and according to current good medical practice. Any medication administered for the treatment of an AE should be recorded in the patient's eCRF.

If the outcome of an AE is not available at the time of the initial report or at study exit (premature or not), follow-up will proceed until outcome is known. All collected data will be recorded in source documents.

8.3.1.2 *Notification and reporting of Serious Adverse Events (SAEs)*

Any SAE, whether deemed drug/procedure-related or not, must be recorded on the corresponding eCRF Form (SAE form), which will, upon completion, be automatically followed by e-mail alerts to Pharmacovigilance-CRO (PV-CRO), Investigator (if completed by Independent Physician), Monitor, Sponsor, and Managing Physician of the Production/Tissue Establishment. In case of technical problem with the eCRF, a paper version of the Form will be sent by fax to the SSO (+ [REDACTED]) who will immediately inform the Managing Physician of the safety event occurrence, and the eCRF will be completed (by the Investigator or Independent Physician) thereafter as soon as possible.

In the event of any SAE, occurring from the Screening Period up to the end of the long term follow-up (48 months after Product Implantation (Visit 3)), the Investigator (or Independent Physician for visit 2) will **within 24 hours of event occurrence or awareness**:

1. the Study Safety Officer (SSO) by phone: Safety Events Phone Number, 24/7 cover:
[REDACTED]
2. Record the SAE on the corresponding eCRF Form (SAE form) or send it by fax [REDACTED]
[REDACTED] or per email ([REDACTED]) to the SSO
who will immediately inform the Sponsor of the safety event occurrence

The eCRF will be completed (by the Investigator or Independent Physician) thereafter as soon as possible.

Briefly, the SAE Form (and the related Follow-up Forms if needed) will include the following information and differentiated assessment:

- Patient identification: Patient Identification Number, age, and sex
- SAE diagnosis and description, start and end dates, concomitant drugs and history

PREOB-ON3 - Clinical Study Protocol

PREOB-ON3-CSP	V 6.1	Author: [name]	May 15, 2017	Pg. 75/76
---------------	-------	----------------	--------------	-----------

- Outcome (recovery with or without sequelae, unchanged, improvement, worsening, death, or other) and action taken (none, patient discontinuation and withdrawal from the study, change in concomitant medication(s) and/or new medication(s), other treatment(s) and/or therapeutic procedure(s) (*i.e.* invasive procedures, surgery, or unknown))
- Criteria for seriousness (death, life-threatening, persistent or significant disability or incapacity, new or prolonged hospitalization, congenital abnormality or birth defect, important medical event), severity (mild, moderate, severe), and frequency (intermittent, continuous, or other)
- Causal relationship with the IMP (assessment of drug-event causal relationship and consistency with applicable product information, e.g., the Investigator's Brochure and evaluated as certain, probable or likely, possible, unlikely, unrelated, unknown or not assessable)
- Causal relationship with the trial procedures, including the bone marrow harvesting and blood sampling, and the product implantation (core decompression, implantation surgery, and general anaesthesia)
- Relationship with the study disease and/or underlying, concomitant, and/or intercurrent diseases, relationship with concomitant medication or treatment, and/or drug interactions
- Suspected or confirmed cases of infection
- Suspected or confirmed cases of ectopic calcification or myositis ossificans
- Unexpected reactions (e.g., hypersensitivity, allergic, immunogenic, autoimmune, and/or toxic)

In Europe

Based on data and information available in both the SAE Form and in the Investigation and Conclusion Report (see below) (and additional queries, if needed), the SSO will notify the occurrence of SUSAR, SAR, and/or SAE related to the trial procedures to both EudraVigilance database and Ethics Committees (all Member States concerned), and to all concerned Investigators and Sponsor in agreement with all applicable legislation.

This notification will be sent by the unblinded SSO to both EudraVigilance database and Ethics Committees while blinding will be preserved for both the Investigators and Sponsor.

In the United States of America

Based on data and information available in both the SAE Form and in the Investigation and Conclusion Report (see below) (and additional queries, if needed), the Sponsor will notify the

PREOB-ON3 - Clinical Study Protocol

PREOB-ON3-CSP	V 6.1	Author: [name]	May 15, 2017	Pg. 76/77
---------------	-------	----------------	--------------	-----------

FDA and all participating investigators in an IND safety report of potential serious risks, including any suspected adverse reaction that is both serious and unexpected.

This notification will be sent by the SSO to the FDA and Investigators.

The Sponsor or designee (PV-CRO) must submit a written summary of the clinical course of any life-threatening SAE and related patient information to the FDA within 15 days. Serious and unexpected ADRs that are not-life-threatening must be reported to the FDA within 15 calendar days. Any serious and unexpected AE (including all deaths) must also be reported to the IRB by the Investigator according to IRB reporting requirements (where applicable) and documentation of this report sent to the Sponsor and designee (PV-CRO).

All SAEs will be followed to resolution, defined as patient's health has returned to his/her baseline status or all variables have returned to normal). If the Investigator does not expect any further improvement or worsening of the event the SAE is followed until stabilization of the event. The event is otherwise explained regard less of whether the patient is still participating in the study.

8.3.1.3 *Notification and Reporting of Serious Adverse Safety/Quality Events (SASQE)*

Based on the information available in the eCRF SAE Form, the Managing Physician will immediately investigate. If the investigation indicates that the safety event is actually related to the procurement, testing, processing, storage, labelling and packaging, delivery, transport, and/or distribution of Investigational Medicinal Product, and/or to the quality and safety of the product the event will then be considered as a serious and unexpected adverse reaction to the product, or SAE related to the trial procedures, and the Managing Physician will within 24 hours of the event occurrence or awareness notify (through an Immediate Notification Report) the CAs and SSO (the Investigator, Monitor, and Sponsor will also be notified via an automatic e-mail alert generated from the eCRF page completed by the Managing Physician).

An Investigation and Conclusion Report - prepared by the Managing Physician - will be sent to the CAs and SSO (with a blind copy sent to the Investigator and Sponsor) as soon as possible and no later than 5 calendar days after knowledge of event for the initial report (or for the additional follow-up reports if needed). The SSO will record this event in the Eudravigilance database.

If the SASQE has occurred during the harvest or implantation procedure in Investigating Site, or between reception of the IMP at the Investigating Site and IMP implantation, the Independent Physician or the Investigator, respectively, will immediately record the relevant information in the corresponding eCRF Form (completion of this Form will be followed by automatic e-mail

PREOB-ON3 - Clinical Study Protocol

PREOB-ON3-CSP	V 6.1	Author: [name]	May 15, 2017	Pg. 77/78
---------------	-------	----------------	--------------	-----------

alerts to the Managing Physician, SSO, Investigator (in case of completion by Independent Physician), Monitor, and Sponsor).

If a serious safety issue is identified, either upon receipt of an individual case report or upon review of aggregate data, the Sponsor will issue a communication to all Investigators as soon as possible. A safety issue that impacts upon the course of the trial, including suspension of the trial, safety-related amendments to the Study Protocol, change or update of Subject Information Sheet and Informed Consent Form or Investigator's Brochure, will also be reported to the Investigators (after prior submission and approval by the CAs and ECs).

8.3.2 Annual Safety Reports – Development Safety Update reports (DSURs)

EU Annual Safety Reports

In addition to the expedited reporting, the SSO will provide annual development safety update reports (DSUR) to CAs, ECs, and Sponsor, including but not limited to all SARs, and/or SAEs related to the trial procedures, together with an overview of all other SAEs, AEs, and SARs that have occurred during the reporting period (in all sites and countries). The report will be provided in the format laid down in Guideline ICH topic E2 F.

IND Annual Safety Reports

In addition to the expedited reporting, the SSO will provide annual development safety update reports for submission to the FDA according to 21 CFR 312.33, including but not limited to all IND safety letters, SARs, and/or SAEs related to the trial procedures, together with an overview of all other SAEs, AEs, and SASQEs that have occurred during the reporting period (in all sites and countries). The report will be provided in the format laid down in Guideline ICH E2 F.

8.3.3 Safety Data Monitoring

The occurrence of AEs, SAEs, and SASQEs will be monitored during the whole study period (from Screening Period) on an ongoing basis by the Study Safety Officer, the Managing Physician of the Production/Tissue Establishment, and the Sponsor. The Sponsor will also receive from the Study Safety Officer a regular detailed updated listing of all AEs, SAEs, and SASQEs.

8.3.4 Data Safety Monitoring Board

An independent data-monitoring committee will be established to assess at intervals the progress of the study, the safety data and the critical efficacy endpoints. This board will

PREOB-ON3 - Clinical Study Protocol

PREOB-ON3-CSP	V 6.1	Author: [name]	May 15, 2017	Pg. 78/79
---------------	-------	----------------	--------------	-----------

recommend to the Sponsor whether to continue, modify or stop the trial. The members of the board will be unblind for the study while the Sponsor and Investigators will remain blind.

8.4 Procedure in Case of Pregnancy

Women included in the study must be post-menopausal (defined as at least 12 months post cessation of menses), surgically sterile or, for women with childbearing potential, using a reliable method of contraception for at least 6 weeks prior to study entry (Screening Period, Visit 1) and during the whole study period. Women with childbearing potential will undergo pregnancy tests at all study visits, and at the last visit to the clinic in case of premature discontinuation. However, if a female patient becomes pregnant during the trial, she will be followed as per study procedure but will **NOT** undergo bilateral X-ray and MRI of the hip.

Any pregnancy will be systematically followed and reported within 24 hours of diagnosis to the Study Safety Officer and Monitor (Pregnancy Form will be immediately completed in the eCRF, with subsequent urgent notification), and their outcomes will be reported to the Study Safety Officer and Monitor.

Any pregnancy will be handled as an SAE regardless the relationship between the Investigational Medicinal Product and the event. Any complication arising during pregnancy will be recorded as an AE and will constitute a SAE if it fulfils any of the specified criteria for a SAE.

At the end of the pregnancy, whether that be full-term or premature, information on the status of the mother and child will be forwarded to Study Safety Officer.

If the outcome of pregnancy is:

- Elective abortions without complications, they will be recorded, documented and reported to the Study Safety Officer and Monitor, but they should not be handled as AEs;
- Any spontaneous miscarriages or abortions for medical reasons, or congenital abnormalities or birth defects, will be recorded, documented, reported, and handled as SAEs and full details will be requested.

8.5 Emergency Procedures

8.5.1 Emergency Contact Procedure

- In case of SAE or any other safety event or medical concern, the following contact will be available (24/7 cover) for continuous support and assistance (Study Safety Officer):

PREOB-ON3 - Clinical Study Protocol

PREOB-ON3-CSP

V 6.1

Author: [name]

May 15, 2017

Pg. 79/80

Emergency and Safety Events Phone Number: [REDACTED]

The Investigator is responsible for ensuring that procedures and expertise are available to cope with medical emergencies during the study. Each patient will receive a Patient Study Card with the name and surname, the Patient Identification Number, Title and Number of the study, type of treatment received (cell product), and Name of the Sponsor. This card will also record the name, surname, full address, and phone number of the Investigator, the address and phone number of the Emergency Room of the Investigating Site, and the Emergency and Safety Events Phone Number (24/7 cover). The aim of this card is to inform any physician having to deal with a patient in an emergency situation that the patient is in a clinical trial and that he/she can contact the trial investigator for more relevant information. Patients will be instructed to carry this card around at any time during the study.

- For any other questions or study information, the following contact will be available (office hours) for continuous support and assistance:

[REDACTED]

[REDACTED]

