2.3.4 Blinding

The study will be conducted double-blind with reference to the evaluation of trial results.

Briefly:

- The only physician to know patient group assignment is the Independent Physician, performing the (sham) bone marrow harvesting procedure.
- Investigators and Patients are blind to treatment assignment. Both patient groups undergo a bone marrow harvest, real or sham, performed by the Independent Physician, and a Core decompression/Implantation procedure performed by the Investigator, following identical procedures.
- The Investigational Medicinal Product, PREOB® and Placebo, are supplied in identical packaging conditions. The final product is packaged in a blind ready to use syringe.
- Radiologists are blind to the group assignment. All images (conventional X-ray, MRI and CT) will be processed to ensure blinding, notably coding and masking of posterior iliac crest through a Centralized Medical Imaging System. Processed images (*i.e.* blind) will be analysed by a single reader (Central Radiologist).
- To ensure the blinding of the study, imaging data should not be distributed to the patient and/or to the blinded study staff. However, if distribution is required (for any reasons), the imaging data should be masked at the harvesting region (iliac crest) prior to distribution, or depending on local Hospital policy.
- Blinding will only be lifted after completion of all study visits from all patients.

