- The date the patient exited the study, and a notation as to whether the patient completed the study or the reason for discontinuation

The WOMAC® subscales are to be completed directly by the patient. The original pages, considered as source data, will be kept and filed on site (in the Investigator's Trial Master File).

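### The study card in Section 8.5.1 records a cell product as the treatment received by every patient, which is untrue for the placebo arm

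*Combined protocol and SAP*

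**What the plan says.** Section 8.5.1 describes the card and does not distinguish between arms: "Each patient will receive a Patient Study Card with the name and surname". Among its contents are "type of treatment received (cell product), and Name of the Sponsor". The patient holds it throughout: "Patients will be instructed to carry this card around at any time during the study". The section limits the card's purpose to telling an emergency physician "that the patient is in a clinical trial and that he/she can contact the trial investigator for more relevant information". The card also shows the study title and number, the Investigator's address and telephone number, the emergency room's details and a 24/7 safety number.

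On blinding, Section 2.3.4 states: "Investigators and Patients are blind to treatment assignment". It adds: "Blinding will only be lifted after completion of all study visits from all patients". Annex 3 likewise lists the patient and the Principal Investigator as blind.

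The only other mention of the card is in Section 12.2, which lists it among the papers sent to ethics committees. No section says that the treatment entry mentions placebo or blinded treatment.

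**The concern.** The entry is worded as a statement of what the patient received, and its only stated content is a cell product. Half of the planned patients receive no cells. The instruction therefore cannot be both true and uniform. A uniform card misstates exposure for placebo patients, and an accurate card would disclose the arm.

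Two things are at stake. The first is the accuracy of a document meant to be read in an emergency by someone who does not know the trial. The second is consistency with the blind, which matters because one of the two components of the primary endpoint is pain reported by the patient: the WOMAC "subscales are to be completed directly by the patient" (Section 11.2). The protocol protects that report with a sham harvest, an Independent Physician and a blind syringe, so a safety document should not be worded in a way that could be read as naming the arm.

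**Working it through.** The protocol states no figure to reproduce on this point. The check compares sections, with one line of arithmetic.

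**Inputs**

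- Recipients of the card: each patient (Section 8.5.1).
- Treatment entry: treatment received, with a cell product as its only stated content (Section 8.5.1).
- Placebo: cell component and cellular concentration not applicable, 5 ml solution (Table 5); 5 ml single dose with no cell count (Table 6).
- Planned size: 118 patients, randomised 1:1 (Synopsis; Section 10.4).
- Access to allocation: the Independent Physician and the Sponsor's Managing Physician obtain it by logging into the eCRF (Section 3.2). Section 2.3.4 says of the treating side: "The only physician to know patient group assignment is the Independent Physician". The Investigator, pharmacist, Sponsor and monitor are blind (Annex 3).
- Emergency unblinding: by the Investigator, through the eCRF, when knowing the allocation could improve or change the patient's management (Section 8.5.2).

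**Reading A: the same entry on every card.** The entry is true for PREOB patients and untrue for placebo patients. Planned number affected: 118 × 1/2 = 59, which is 59/118 = 50% of cards. A uniform entry carries no information about the arm, so the blind is intact.

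**Reading B: the entry filled in by arm.** The entry is true for everyone, but the patient and anyone shown the card learn the allocation. That conflicts with Section 2.3.4, Annex 3 and the rule in Section 8.5.2 against breaking the code.

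**Which reading fits the text.** Section 8.5.1 gives one fixed content and no alternative for placebo. It does not say who prepares the card, and no section passes the allocation to anyone for that purpose. The Investigator, whose details are on the card, is blind. Reading A is much the likelier, and its consequence is a wrong statement, not a broken blind.

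**Does another section repair it?** No. Section 12.2 only names the card. Section 8.5.2 gives a route to the true allocation but does not change what the card says.

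**The case against.** The strongest defence is that the words in brackets name the class of product under study, not what the individual patient received. Where Section 8.5.2 means the arm, it speaks of assignment, allocation or code, and Section 8.5.1 presents the card as a pointer to the Investigator, not as an exposure record. Consent under Section 2.3.1 covers random assignment, so patients know that they may have received placebo. An emergency physician has the Investigator's number and the 24/7 line, and Section 8.5.2 allows unblinding if it would matter. Finally, the printed card and the study title on it are not in the documents, and the title may itself convey the blinded design.

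Much of this stands. It limits the practical harm and rules out a claim that the issued cards are known to be wrong. It does not rescue the wording: the entry is described as treatment received, and nothing in the protocol says that it means the product class. The instruction governing the card should be right on its face.

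A reader might go further and infer that the card unblinds the whole trial and so biases patient-reported pain and the primary comparison. The documents do not support this. It needs Reading B, which conflicts with the fixed wording and with the limited access to allocation. Even then, nothing in the documents gives a size for any shift in responder rates.

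**Conclusion.** The concern holds as a minor error: the instruction in Section 8.5.1 is wrong as written. On the likeliest reading the treatment entry is untrue for the placebo arm, 59 of 118 planned patients. That count assumes one uniform card, printed as Section 8.5.1 describes it, and the planned 1:1 allocation; the actual number depends on recruitment and on the printed text, which cannot be checked here.

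Filling in the entry by arm would contradict the blinding rules. The text does not exclude that possibility, but it does not show that it is planned.

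**What to change.** In Section 8.5.1, replace the treatment entry with one wording for all cards, for example *double-blind study of autologous osteoblastic cells (PREOB) or placebo*. Keep the existing contacts. Add a reference to Section 8.5.2 for unblinding. The new wording should not suggest that the allocation can be obtained from the safety telephone line, since Section 8.5.2 has the Investigator unblind through the eCRF under stated conditions.

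Then check the printed card. If it already conveys that the treatment is blinded and may be placebo, only the protocol text needs correcting. If it carries the present wording, reissue it.

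The cost is one phrase in the protocol and, if needed, a reprint and resubmission of the card. Study procedures, sample size and analysis are unchanged.
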